| | 
 If the groin ultrasound is negative/normal (n=180), participants will be randomised 2:1 to receive either a groin LND (n=60) or bilateral groin USM every 2 months along with clinical examination every 3 months for a period of 12 months (n=120; no upfront groin LND). 
All participants will receive appropriate surgical excision of the primary tumour (radical wide local excision or radical vulvectomy). All lymph nodes will undergo central pathology review [1]. Postoperative treatment will follow local institutional treatment guidelines.
 |
| 
Stage details and number of participants
 | 
240 participants in total:
 
 Ultrasound negative/normal groin nodes (120 undergoing groin USM every 2 months along with clinical examination every 3 months and 60 upfront groin IFL/SNB) Ultrasound suspicious/indeterminate groin nodes (60 having upfront groin IFL/SNB) |
| 
Study Duration
 | 
Enrolment for this study is projected to conclude within a 4-year timeframe. The study will be deemed complete once 180 participants have been enrolled, randomised, and successfully completed a 12-month follow-up period.
 |

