An overall assessment will be made by the radiologist into normal or suspicious/positive. Radiologists will send their report to the local PI within 5 working days of ultrasound completion. All sites are required to enter the completed ultrasound eCRF on REDCap within 5 working days of ultrasound completion. Additionally, they must upload a copy of a signed and de-identified ultrasound report to REDCap, where QCGC Research will verify ultrasound completion.

If the participant is randomised to serial groin USM, patients will have surgical excision of the primary vulvar tumour followed by bilateral groin ultrasound every two months and clinical examinations every three months for the 12 months.

If suspicious, indeterminate, or positive nodes or any other concerning indicators are detected, the participant will be referred to either the local PI or the specialist gynaecological oncologist to discuss their options. Depending on the clinical judgment of the clinician, the participant may be recommended for LND (standard treatment) or may opt to continue with bilateral groin ultrasound every two months and clinical examinations every three months (remaining on trial). Participants undergoing LND will no longer need bilateral groin ultrasound and blood collections every two months and clinical examinations every three months. However, their data will still be collected up to the original 12-month point. Data collected will include documentation of the status of disease, AEs, pain level, health status and quality of life and lymphoedema. Please refer to section [10.6.5.1](#), titled 'Evaluating and Reporting Positive Nodes', for further information.

Patients that fail to comply with the serial ultrasound and clinical examination schedule will be removed from the trial and referred back to their gynaecological oncologist for alternative treatment for safety reasons.

7. Project Methodology

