7.5 Follow-Up (Visits 4-9)

All enrolled participants, irrespective of treatment group will be followed-up for 12 months. Participants without groin LND will be provided with medical imaging request forms to receive groin ultrasound examinations every 2 months. **Changes in ultrasound patterns from “normal” to “suspicious” will alert the gynae-oncologist and trigger further clinical action, such as groin LND and histological assessment of the groin nodes. Groin USM will not be offered to women who had a groin LND (IFL or SNB) as it is not standard practice for these patients.** If ultrasound scan surveillance following sentinel node biopsy is included in the standard care protocol at any of the study sites, participants randomised to lymph node dissection (LND) can undergo ultrasound scans as part of their standard care, though it is not mandatory for this study.

Participants will be assessed for local, regional, or distant recurrence, quality of life status, and treatment morbidity for 12 months. Data collected will include documentation of the status of disease, AEs, pain level, health status, quality of life and lymphoedema.

Participants randomised to serial groin USM will be seen every 3 months by a gynaecological oncologist or gynaecologist for clinical examination as per routine standard. Participants receiving standard groin LND (either SNB or LND) will be seen at 8 weeks, 3, 6, 9 and 12 months as per standard clinical practice. Follow up will be handed over to the treating gynaecological oncologist after 12 months.

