10.6.5.1 Evaluating and Reporting Positive Nodes

The senior medical imaging specialists will review the serial high-resolution bilateral ultrasound scans, evaluating for the presence of positive lymph nodes or any suspicious findings, relying on their clinical expertise. Radiologists will send their report to the local PI within 5 working days of ultrasound completion. All sites are required to enter the completed ultrasound eCRF on REDCap within 5 working days of ultrasound completion. Additionally, they must upload a copy of a signed and de-identified ultrasound report to REDCap, where QCGC Research will verify ultrasound completion. All sites should also provide a copy of de-identified US images to QCGC Research through The University of Queensland Research Data Manager platform (UQRDM) for quality assurance purposes. UQRDM is a secure platform designed for storing, managing, and sharing research data. It ensures compliance with data protection regulations and facilitates efficient data access and collaboration among researchers.

As explicitly stated in section [6.5.3](#) of the protocol, if suspicious, indeterminate, or positive nodes or any other concerning indicators are detected, the participant will be referred to either the local PI or the specialist gynaecological oncologist to discuss their options. Depending on the clinical judgment of the clinician, the participant may be recommended for LND (standard treatment) or may opt to continue with bilateral groin USM every two months and clinical examinations every three months (remaining on trial).

Participants receiving interventional treatment (serial groin USM in conjunction with clinical examination) who develop suspicious, indeterminate, or positive nodes are not removed from the trial as we still collect their data. The requirement for bi-monthly bilateral ultrasound, physical examination and blood tests will be discontinued.

11. Statistical Considerations

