11.2 Statistical Analysis

Analyses will adhere to the intention-to-treat principle and a Statistical Analysis Plan will be prepared using the estimand framework (ICH E9-R1 addendum).

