12.7 Missing Ultrasound or Physical Examination

If a participant allocated to the interventional group misses their ultrasound appointment or physical examination by ± 7 days, both the trial PI and the site will be notified. The PI will investigate, with trial management assisting in promptly rescheduling the ultrasound appointment or physical examination within 7 days. Actions will be implemented to mitigate the risk, which may include the possibility of removing the patient from the trial.

We will allocate dedicated staff to ensure participants adhere to and comply with all study monitoring schedules, ensuring ultrasound scan appointments or physical examinations are conducted within a ± 7 -day window, and that all eCRFs and reports are promptly received. Should any issues arise, the site PI will be immediately informed.

13. Dissemination of Findings

We expect the results of this study will be disseminated by publication in a peer reviewed journal, presentation at national or international conferences, and circulation throughout patient and professional organisations relevant to gynaecological oncology care. The investigators agree that publications or presentations of any of the results from the study will take into account the co-operative nature of the conduct of the study and the overall objective of increasing public knowledge and shall be in accordance with accepted scientific practice, academic standards and customs and in accordance with the protocol and with any more specific publication/presentation guidelines developed by the trial management committee during the course of the study, including but not limited to the following:

As the study is a multi-centre study, any results from a single centre must not be published before the publication of results from all centres and before the trial PI does not give explicit written permission to the site/investigator to do so.

Individuals making a substantial contribution to the study will be recognised with co-authorship in publications from the study unless they elect not to be recognised.

14. Ethical Consideration

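### Ultrasound-arm women who miss surveillance are to be removed from the trial, and the protocol does not secure their month-12 outcome, on which the safety decision rests

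*Protocol*

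**What the plan says.** Section 6.5.3 sets a mandatory rule for women on the scan and examination schedule: "Patients that fail to comply with the serial ultrasound and clinical examination schedule will be removed from the trial". They are referred back to their gynaecological oncologist, and nothing is said about collecting their outcome afterwards.

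Section 12.7 covers the same situation differently. After a missed visit the PI investigates and the visit is rescheduled within 7 days. Then: "Actions will be implemented to mitigate the risk, which may include the possibility of removing the patient from the trial".

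Other women who leave surveillance are treated differently. Those who go on to lymph node dissection (LND) are kept under 6.5.3: "However, their data will still be collected up to the original 12-month point". Section 10.6.5.1 says that USM women with suspicious, indeterminate or positive nodes "are not removed from the trial as we still collect their data".

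Three general statements bear on this:

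- Section 7.5: "All enrolled participants, irrespective of treatment group will be followed-up for 12 months".
- Section 11.2: "Analyses will adhere to the intention-to-treat principle".
- Synopsis, Study Duration: the study is complete "once 180 participants have been enrolled, randomised, and successfully completed a 12-month follow-up period".

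Sections 11.1 and 11.2.1 base the safety declaration on P(recur|USM), estimated in the USM arm alone. The stopping boundaries use the same quantity.

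**The concern.** Section 10.6.5.1 gives continued data collection as the reason why certain women are not removed. On the protocol's own usage, then, removal means that outcome collection stops. An outcome that was never collected cannot be analysed by intention to treat, and no later analysis plan can recover it.

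The loss may not be neutral. Section 12.1 names the risk of the intervention as a groin recurrence that grows large without being detected, and presents the scans and examinations as the mitigation. A woman who misses them is without that mitigation, so non-compliance may be related to the primary event. The rule also touches only the arm that decides the trial. If removed women have more events than the others, the observed rate describes adherent women rather than the strategy that Section 5.2 asks about, and the stopping boundaries see fewer events than occurred.

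**Working it through.** **Inputs from Section 11.1.** Safety is declared if Pr[P(recur|USM) < 0.06] is 80%. The trial stops if Pr[P(recur|USM) > 0.06] exceeds 70%, stated as 5/40, 6/60, 7/80, 9/100 or 10/120. The assumed true rate is 3%. The stated properties are less than 2% wrong early stopping and 0.85 probability of declaring safety at N=120. The prior is described only as informed by 1/32.

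**Reproducing the plan's figures.** The prior parameters are not given, so they are inferred. Beta(1.5, 31.5), which is a Jeffreys Beta(0.5, 0.5) prior updated with 1 event and 31 non-events, has posterior Beta(1.5 + x, 31.5 + n − x). It returns exactly the five stated boundaries. At N=120:

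- x = 5: Pr(rate < 0.06) = 0.859, safe.
- x = 6: Pr(rate < 0.06) = 0.758, not safe.

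An exact binomial recursion over looks at 40, 60, 80, 100 and 120 gives, at a true 3%, early stopping of 0.017 and a declaration of safety of 0.847. Both agree with the protocol.

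**One lost event.** With all 120 women counted, 6/120 has posterior 0.758 and fails. If one woman with an event is removed and her outcome is not collected, the data are 5/119, with posterior 0.855, and the arm passes.

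**Effect of removal.** Hold the true whole-arm rate at p = 0.06. Let a fraction q be removed, with RR times the compliers' risk. The compliers' risk is p_c = p / (1 − q + q·RR), and the removed women's risk is RR·p_c. For example, q = 0.10 and RR = 3 give p_c = 0.06/1.20 = 0.050 and 0.150. Neither q nor RR is in the protocol; both are assumptions.

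With everyone counted, P(declare safe) at 6% is 0.267.

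| q | RR | compliers | removed | replaced, ≤5/120 | dropped (limit) |
|---|---|---|---|---|---|
| 5% | 2 | 5.71% | 11.43% | 0.312 | 0.360 (5/114) |
| 5% | 3 | 5.45% | 16.36% | 0.356 | 0.405 (5/114) |
| 10% | 2 | 5.45% | 10.91% | 0.356 | 0.293 (4/108) |
| 10% | 3 | 5.00% | 15.00% | 0.441 | 0.368 (4/108) |
| 15% | 2 | 5.22% | 10.43% | 0.399 | 0.380 (4/102) |
| 15% | 3 | 4.62% | 13.85% | 0.520 | 0.490 (4/102) |
| 20% | 2 | 5.00% | 10.00% | 0.441 | 0.473 (4/96) |
| 20% | 3 | 4.29% | 12.86% | 0.590 | 0.606 (4/96) |

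If removed women stay in the denominator as event-free, the same grid gives 0.36 to 0.77.

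**Removal unrelated to risk (RR = 1).** Replaced: 0.267, unchanged. Dropped: 0.313, 0.217, 0.261 and 0.311 at n = 114, 108, 102 and 96. The estimate is unbiased; those figures move only because the pass limit is a whole number (5/108 has posterior 0.7998, just short of 80%). Counting removed women as event-free still raises the chance, for example to 0.365 at q = 10%.

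**The case against.** A reader might infer that the protocol takes its highest-risk women out of the safety estimate and fills their places with compliers. The documents do not support that in full.

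- Section 12.7 does not mandate removal. A missed visit leads first to investigation and rescheduling, with dedicated staff, so few women may be removed.
- No section says that removed women are excluded from the primary analysis. Section 11.2 promises intention to treat and an analysis plan using estimands, 12.1 monitors recurrences in all groups, and 12.5 adjudicates every reported recurrence. The loss of data is read from the wording of 10.6.5.1.
- No replacement procedure exists. The Study Duration sentence leaves room for replacement but does not order it.
- That non-compliers are at higher risk is an inference from 12.1.
- Large assumed risks strain the pilot data in 3.4, where any positive node occurred in 3/32 (9.4%) over a median of 37 months. The primary event is narrower, and removed women are referred for other treatment. With compliers at 3% and 10% removed at 9.4%, the arm rate is 0.9 × 3% + 0.1 × 9.4% = 3.6%. P(declare safe) is then 0.73 with everyone counted, against 0.85 without the removed women, and declaring safety would be correct.

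All of this stands as a limit on size and certainty. It does not remove the contradiction. An estimand can say how non-adherence is handled, but it needs outcomes that 6.5.3 gives sites no instruction to collect.

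**Conclusion.** The point holds as a contradiction with a possible bias of unknown size. Sections 6.5.3 and 12.7 disagree on whether removal is mandatory. Removal as 10.6.5.1 uses the word conflicts with 7.5 and 11.2. The bias runs towards declaring safety if removed women carry above-average risk, or if they are counted as event-free; it is absent if removal is unrelated to risk and they are dropped or replaced.

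The range of 0.29-0.61 against 0.27 rests on four assumptions: the inferred prior, a true rate at the 6% limit rather than the design's 3%, 5-20% removed, and 2-3 times the compliers' risk. The implied 10-16% risk in removed women lies above the pilot's 9.4%. The matter still deserves correction before outcomes are lost, because the verdict can turn on a single event and uncollected outcomes may not be recoverable.

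**What to change.** 1. Reconcile Sections 6.5.3 and 12.7 on when a woman leaves protocol surveillance. Which clinical rule applies is for the investigators, and this review does not choose it.
2. In both sections, state that leaving surveillance is not leaving the trial. Unless the woman withdraws consent, her groin status is recorded to month 12, and she is counted in her randomised arm in the primary analysis and in the stopping boundaries. The clinical referral wording can stay.
3. In Study Duration, define completion as 180 women randomised and followed to month 12, death or withdrawal of consent, so that removed women are not replaced by completers.

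The cost is a short amendment, a few month-12 status checks, and possibly a less favourable observed rate. Retention is already practised in this trial for women who go on to LND.

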7.1 Study Procedures and Assessments

Prospective participants will be screened at the gynaecological oncology clinic based on the above inclusion and exclusion criteria. Prospective participants are identified based on this criterion by Investigators and/or research staff. Once a prospective participant has been identified as being potentially eligible, a member of the clinical care team will approach the participant, enquire if they consent to being contacted by a research team member regarding the study, and provide them with an information pack containing the Participant Information and Consent Form (PICF). Subsequently, the prospective participant will either be approached in person by a research team member or contacted later via phone or email to discuss the study. Each prospective participant will be given a full explanation of the study and will be given adequate time to thoroughly read the PICF and discuss with family and friends (if applicable) prior to agreeing to participate. Time for questions throughout the discussion will be given and all questions will be adequately addressed before proceeding. The participant will not be coerced to participate in the study. Participants may choose to consent on the same day as being given the PICF, provided the member of staff taking consent is satisfied that the participant understands the study. Alternatively, prospective participants will be provided with the option to take the PICF home for further consideration and return the signed consent form via express post (envelopes to be provided by the site).

Prospective patients will be informed that they are free to refuse participation in this study and, if they choose to participate, that they may withdraw from the study at any time without compromising their medical care. Participants who agree to the study will be provided with a copy of the information sheet and their signed consent form. Participant data will be collected over the period of the study. This may be obtained from the participants themselves, other health institutions, medical practices,

laboratory results etc. No third party will be provided with access to any data on participants. Consent to obtain this information will have been provided by participants when they sign the consent form. No data is collected/retained on participants prior to this.

7.2 Pre-Operative (Visit 1)

7.2.1 Screening/Baseline

The following procedures will be performed within 75 days prior to surgery:

- Screen eligibility of patients (see section 6.1 Study Population)
- Histologically confirmed SCC, adenocarcinoma, or melanoma of the vulvar without evidence of regional or distant metastatic disease (clinical Stage 1b or 2)
- CT or MRI of Chest, Abdomen and Pelvis
- Sign HREC approved informed consent form

The following procedures will be performed within 30 days prior to surgery:

- Physical examination
- Negative (serum or urine) pregnancy (BHCG) test ONLY in pre-menopausal women and women < 2 years after the onset of menopause
- Standard preoperative laboratory workup as determined by each institution (e.g. full blood count (FBC), liver function tests (LFT's))
- Record all current medications
- Record surgical, medical, and gynaecological history
- Review Eastern Cooperative Oncology Group (ECOG) performance score
- Assess participants for their individual pain level using Numeric Pain Rating Scale
- Height and Weight to calculate Body Mass Index (BMI) = kg/m²
- Lymphoedema assessments via bioimpedance spectroscopy (BIS), leg circumference measurements (participating sites only) and/or Self-Report Questionnaire
- Provide participant with Baseline Questionnaire booklet (demographics, PROMs, HRQL, lymphoedema).

7.3 Ultrasound (Visit 2)

- Participants will undergo a groin ultrasound examination up to 30 days prior to planned surgery.
- Following review of the ultrasound images, patients with negative/normal groin ultrasound will be randomised.
- Notify the participants' primary care physicians if they are assigned to the Interventional Group (with bi-monthly groin USM in conjunction with clinical examination every three months).
- Optional blood sample for translational research (baseline) for all consented participants

7.4 Surgery (Visit 3)

- Perform surgical excision of the primary vulvar tumour (radical wide local excision or radical vulvectomy)
- If participant is receiving groin LND, perform IFL or SNB according to local clinical practice management guidelines
- Record all intraoperative information (including operation details, length of surgery, intraoperative complications, transfusion details and any other special conditions around the operation)
- Record histopathology findings

7.5 Follow-Up (Visits 4-9)

All enrolled participants, irrespective of treatment group will be followed-up for 12 months. Participants without groin LND will be provided with medical imaging request forms to receive groin ultrasound examinations every 2 months. **Changes in ultrasound patterns from “normal” to “suspicious” will alert the gynae-oncologist and trigger further clinical action, such as groin LND and histological assessment of the groin nodes. Groin USM will not be offered to women who had a groin LND (IFL or SNB) as it is not standard practice for these patients.** If ultrasound scan surveillance following sentinel node biopsy is included in the standard care protocol at any of the study sites, participants randomised to lymph node dissection (LND) can undergo ultrasound scans as part of their standard care, though it is not mandatory for this study.

Participants will be assessed for local, regional, or distant recurrence, quality of life status, and treatment morbidity for 12 months. Data collected will include documentation of the status of disease, AEs, pain level, health status, quality of life and lymphoedema.

Participants randomised to serial groin USM will be seen every 3 months by a gynaecological oncologist or gynaecologist for clinical examination as per routine standard. Participants receiving standard groin LND (either SNB or LND) will be seen at 8 weeks, 3, 6, 9 and 12 months as per standard clinical practice. Follow up will be handed over to the treating gynaecological oncologist after 12 months.

7.5.1 Postoperative Week 8 ± 3 days (Visit 4) - All Participants

Can be obtained via medical visit, telephone contact or postal correspondence:

- Provide participant with booklet containing PROMS, HRQL and lymphoedema questionnaires
- Lymphoedema assessments via BIS and leg circumference measurements (participating sites only) and/or Self-Report Questionnaire
- Review ECOG performance score
- Assess participants for their individual pain level using Numeric Pain Rating Scale
- Record disease status
- Collect all AEs (assess using Common Terminology Criteria for Adverse Events (CTCAE) V5.0)
- Record hospitalisations
- Record FBC, Urea and Electrolytes and LFT's if available
- Collect all serious adverse events (SAEs)
- Update new medications since surgery

- Optional post-operative translational research blood collection for all consented participants
- Serial high-resolution groin ultrasound (interventional treatment)
- Evaluate symptoms and conduct a physical examination in alignment with European Society for Medical Oncology (ESMO) guidelines.

